## 1.4.2 Pivotal bioequivalence Phase I study

In a previous Phase I, single-centre, open-label, 3-treatment, 2-sequence, 5-period, replicate, randomised cross-over, comparative bioavailability study with evaluation of food effect in healthy male and female non-smokers, primarily the bioavailability of plasma riluzole after single dose of the test formulation compared with that of Rilutek® 50 mg tablets available in USA and secondarily the safety and tolerability of the test formulation and the effect of food on the pharmacokinetics of riluzole were investigated (6).

A total of 32 subjects were enrolled and 30 subjects completed the study. Three (3) treatment conditions were studied: the test formulation administered without water under fasting conditions (Treatment A); Rilutek® 50 mg tablets available in USA administered with water (Treatment B) and the test formulation without water under fed conditions (Treatment C).

Each subject received a total of 3 treatments in 5 periods: Treatment A and Treatment B under fasting conditions in Periods 1-4 according to the randomised replicate cross-over design. All subjects received Treatment C in Period 5.

Blood samples were collected at pre-dose and 0.25, 0.50, 0.75, 1, 1.5, 2, 3, 4, 6, 8, 12, 16, 24, 36, 48, 72, 96, and 120 h post-dose in each study period.

Table 1.4.2.1 Mean main PK parameters of plasma riluzole after Treatments A and B and the outcome of their statistical comparisons

		Geometric LSM					
		Riluzole	Rilutek with 240 mL		90% Geo	metric CI	050/ 1170
Parameter	CV wr	orodispersible film without water (A)	water (B)	Ratio	Lower	Upper	95% upper confidence bound
AUC 0-t (ngxh/mL)	12.65	780.01	714.48	109.17%	105.67%	112.79%	-
$\begin{array}{c} AUC_{0\text{-}\infty} \\ (ngxh/mL) \end{array}$	12.49	795.98	730.02	109.04%	105.58%	112.61%	-
C max (ng/mL)	32.66	-	-	115.82%	-	-	-0.0123

 $AUC_{0-\infty}$ =area under the concentration-time curve from time 0 (dosing) extrapolated to infinity;  $AUC_{0-i}$ = area under the concentration-time curve from time 0 (dosing) to time of last measurable riluzole; CI=confidence interval;  $C_{max}$ =maximum observed plasma concentration; LSM=least-squares mean;  $CV_{WR}$  = within-subject variability for the reference product; ratio = point estimate for geometric mean ratio; CI = confidence interval according to the reference-scaled bioequivalence approach; source: Clinical Study Report 162020

The ANOVA performed on the primary riluzole PK parameters clearly demonstrated the bioequivalence of the novel riluzole orodispersible film to Rilutek  $^{\circledR}$  50 mg tablets available in US.  $CV_{WR}$  of plasma riluzole  $AUC_{0-t}$  and  $AUC_{0-\infty}$  was less than 30% and since their 90% geometric confidence interval (CI) were respectively 105.67% to 112.79% and 105.58% to 112.61% both falling within the acceptance range of 80.00% to 125.00%, test and reference formulations were bioequivalent in terms of extent of exposure to riluzole.

Since  $CV_{WR}$  of  $C_{max}$  was higher than 30%, a scaled average bioequivalence approach was used according to the FDA guidance on bioequivalence studies. Therefore, also in terms of rate of absorption of plasma riluzole, the hypothesis of bioequivalence of test and reference formulation was accepted, because the 95% upper confidence bound was  $\leq 0$  and the geometric mean ratio was within the interval 80.00% to 125.00%.

#### 1.5 Risks and benefits

Riluzole is a known drug which has been used for decades. It is usually well tolerated. Adverse events (AEs) reported in the 3 previous single-dose clinical studies in healthy volunteers of the same test formulation are: somnolence, nausea, oral hypoaesthesia, oral mucosa erythema, dizziness and transiently altered laboratory parameters. Undesired effects reported after stable therapy with the reference formulation include malaise, nausea, high alanine aminotransferase (ALT) values, headache, abdominal pain, pain, vomiting, dizziness, tachycardia, somnolence and circumoral paraesthesia. For details refer to the IB (6).

#### **CONFIDENTIAL**

Study protocol CRO-PK-20-344 Sponsor code Z7251J01 Riluzole orodispersible film replicate bioavailability Final version 1.0, 28APR20

Blood sampling with cannula insertion may cause minor discomfort. The risks associated with blood draws include pain, bleeding and bruising.

No specific benefits for the participants in the current study are foreseen. Their remuneration will be paid after study completion. The remuneration covers loss of time and any inconvenience caused by the participation in the study.

# 2 STUDY OBJECTIVES

The objective of the study is to compare the pharmacokinetic profile of riluzole after replicate single dose of the novel orodispersible film test formulation and of the marketed reference Rilutek® tablets and to evaluate their bioequivalence.

## 2.1 Primary end-point

 $\triangleright$  To evaluate the bioequivalent rate ( $C_{max}$ ) and extent ( $AUC_{0-t}$ ) of absorption of riluzole after replicate single dose administration of test and reference.

# 2.2 Secondary end-points

- ➤ To describe the PK profile of riluzole after replicate single dose administration of test and reference;
- > to evaluate the test product palatability;
- ➤ to collect safety and tolerability data of test and reference after replicate single dose administration.

# 3 CLINICAL SUPPLIES

#### 3.1 Treatment

The subjects will receive single oral doses of 50 mg of riluzole, as test orodispersible film and reference film-coated tablets under fasting conditions, in each of 4 subsequent periods separated by wash-out intervals of at least 7 days between consecutive administrations, according to a 2-treatment, 4-period, replicate cross-over design.

## 3.1.1 Description of products

The analytical certificates will be supplied with the investigational medicinal products (IMPs) and enclosed in the final study report.

## 3.1.1.1 Test product

TEST (T)

IMP Riluzole 50 mg orodispersible film, Aquestive Therapeutics, USA Manufacturer Glenmark Life Sciences, [name],

(active substance) [name]

(GMP compliant)

Manufacturer Aquestive Therapeutics, Inc, [name],

(finished product) Indiana, 46368, USA

(GMP compliant)

QP release: Aquestive Therapeutics, Inc, [name],

46368, USA

(GMP compliant)

Pharmaceutical form: Orodispersible film

Dose 50 mg

Administration route: Supralingual

The qualiquantitative composition of the test is shown in the table below.

Table 3.1.1.1 Quantitative composition of the test IMP

Component	% Solids (w/w)
Riluzole	27.62
Polacrilex Resin	35.18
Polyethylene oxide	1.05
Pullulan	19.24
Hypromellose, substitution type 2910	4.08
Xanthan Gum	0.31
Sucralose	1.57
Xylitol	5.49
Fructose	1.05
Glycerin	2.09
Glycerol Monooleate, Type 40 (GMO)	1.67
Flavor Honey 151a39	0.46
Flavor Juicy Lemon 160a04	0.16
FD&C Yellow #5	0.03
Purified Water	NA

Abbreviations: FD&C=Food, Drug, and Cosmetic (Act); NA=not applicable; w/w=weight per weight.

## 3.1.1.2 Reference product

REFERENCE (R)

IMP Rilutek®, 50 mg riluzole tablets Marketing Authorisation Sanofi Mautre IP, France

Holder

Pharmaceutical form Film-coated tablets

Dose 50 mg Administration route Oral

# 3.1.2 Dose regimen

Four single doses of 50 mg of riluzole (2 as test and 2 as reference formulation) will be administered to each volunteer in 4 subsequent study periods, separated by wash-out intervals of at least 7 days.

## 3.1.3 Route and method of administration

Each study dosing was performed in the morning at  $08:00 \pm 1$  h under fasting conditions. The test formulation will be administered supralingually and the reference orally.

## 3.1.3.1 Test formulation

The study staff will check subjects' mouth to ensure a clean mouth before study drug administration. This will be documented in specific forms.

Before each administration, the subjects will drink 20 mL of still mineral water in order to wet their mouth.

Afterwards, using gloves, the investigator or deputy will take the orodispersible film (32.0x22.0 mm) out of the provided pouch and place the product directly on the top surface (dorsal aspect) of the subjects' tongue. The subjects will close their mouth in a natural way and gently rub the film with the tongue against the roof of the mouth to promote melting and disappearance of the film. The subjects will be allowed to swallow saliva but not to chew, bite, or swallow the film. After the subjects indicate a complete dissolution of the film (confirmed by visual inspection) by raising their hand, they will be allowed to swallow any remaining saliva. The study staff will visually inspect the films 1, 2 and 5 min post-dose until either complete dissolution is confirmed or until the subject alerts the study staff to dissolution of the film. This will be documented in specific forms. If the film is not completely dissolved within 5 min, the subjects will be allowed to swallow without water.

Dosing time is defined as the time the film is placed on the subject's tongue. The study staff will record the actual time of film placement and the actual time of dissolution. If, upon inspection, the film is dissolved, the time of mouth check will be recorded as time of dissolution.

In case a subject chews or moves the film before its complete dissolution, this occurrence will be noted. During the 5-min observation period, the subjects will inform the study staff in case

the film is accidentally swallowed before its complete dissolution and the staff will record the time the film is swallowed.

Dosing, dissolution and accidental swallowing times will be recorded in specific forms and in the subject's CRF.

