# 10.4 Drug administration and analysis of film dissolution

The date and time of film placement, of film dissolution, of accidental film swallowing and reference tablet administrations will be listed. Dosing time is defined as the time the film is placed on the subject's tongue.

The actual time of film dissolution will be summarised by descriptive statistics.

The dose per body weight of riluzole will be listed and summarised by descriptive statistics. The body weight collected at the screening visit will be used for the calculation.

The minimum and maximum number of days of wash-out between periods will be presented.

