Statistical analysis plan CRO-PK-20-344 Sponsor code Z7251J01 Riluzole orodispersible film replicate bioavailability Final version 1.0, 31MAY21

Table 14.2.4.1 - Descriptive statistics of dissolution time (Safety set)

			Safety Set			
		Statistics	Riluzole 50 mg orodispersible film (T) 1 st adm. N=XX	Riluzole 50 mg orodispersible film (T) 2 nd adm. N=XX		
Was the film accidentally swallowed within 5 min after dosing?	Yes	n (%)	nn (xx.x)	nn (xx.x)		
	No	n (%)	nn (xx.x)	nn (xx.x)		
Was the film undissolved at 5 min after dosing and had to be swallowed?	Yes	n (%)	nn (xx.x)	nn (xx.x)		
	No	n (%)	nn (xx.x)	nn (xx.x)		
Dissolution Time [min]		Ν	nn	nn		
		Mean	XXX.XX	XXX.XX		
		SD	XXX.XX	XXX.XX		
		CV%	XXX.XX	XXX.XX		
		Min	XXX.X	XXX.X		
		Median	XXX.XX	XXX.XX		
		Max	XXX.X	XXX.X		

Note: Subjects are summarised according to the product they actually received

The number and the proportion of subjects for each question are reported

The denominator for calculating the proportions is the number of subjects in the safety set of Riluzole 50 mg orodispersible film (T) of each administration

Source: Listing 16.2.5.1 - Investigational medicinal products administration

Statistical analysis plan CRO-PK-20-344 Sponsor code Z7251J01 Riluzole orodispersible film replicate bioavailability Final version 1.0, 31MAY21

Table 14.2.4.2 - Contingency tables of palatability - Safety set

		Safet	Safety Set			
Time Point	Palatability Score	Riluzole 50 mg orodispersible film (T) 1 st adm. N=XX	Riluzole 50 mg orodispersible film (T) 2 nd adm. N=XX			
Immediately after administration	0 - very unpleasant	xx (xx.x)	nn(xx.x)			
	1 - unpleasant	xx (xx.x)	nn (xx.x)			
	2 - acceptable	xx (xx.x)	nn (xx.x)			
	3 - good	xx (xx.x)	nn (xx.x)			
	4 - very good	xx (xx.x)	nn (xx.x)			

Note: The number and the proportion of subjects for each classification level are reported

The denominator for calculating the proportions is the number of subjects in the safety set of Riluzole 50 mg orodispersible film (T) of each administration Source: Listing 16.2.6.2 - Palatability

Statistical analysis plan CRO-PK-20-344 Sponsor code Z7251J01 Riluzole orodispersible film replicate bioavailability Final version 1.0, 31MAY21

Table 14.3.1.1 - Global incidence of subjects with treatment-emergent adverse events - Safety set

	Riluzole 50 mg orodispersible film (T) N=XX n (%) [n AE]	Safety Set Rilutek®, 50 mg riluzole tablets (R) N=XX n (%) [n AE]	Overall N=XX n (%) [n AE]

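### The film dissolution-time statistics cover only films seen to dissolve within about 5 min and treat check times as exact, so the mean, median and maximum may mislead in either direction

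*Protocol*

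**What the plan says.** Protocol 3.1.3.1 gives two routes to a dissolution time.

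- **Subject's signal.** The wording is "After the subjects indicate a complete dissolution of the film (confirmed by visual inspection) by raising their hand". Staff have a general duty: "The study staff will record the actual time of film placement and the actual time of dissolution". A signalled time can fall at any moment.
- **Scheduled check.** "The study staff will visually inspect the films 1, 2 and 5 min post-dose until either complete dissolution is confirmed", or until the subject alerts staff. For a film found gone at a check: "If, upon inspection, the film is dissolved, the time of mouth check will be recorded as time of dissolution".

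Two groups have no dissolution time. For slow films, "If the film is not completely dissolved within 5 min, the subjects will be allowed to swallow without water". For the other group, the subject reports if "the film is accidentally swallowed before its complete dissolution and the staff will record the time the film is swallowed". Neither document assigns a dissolution time or a censoring value to either group, and protocol section 10 treats unavailable data as missing.

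Protocol 10.4 plans: "The actual time of film dissolution will be summarised by descriptive statistics". SAP 8.5 says the same and points to Table 14.2.4.1. That shell shows, for the first and second film administration, yes/no counts for accidental swallowing within 5 min and for the question "Was the film undissolved at 5 min after dosing and had to be swallowed". Below them come N, mean, SD, CV%, minimum, median and maximum of dissolution time. There is no footnote on which films the statistics cover. Listing 16.2.5.1 shows dissolution end times to the second, with no column for whether a time was signalled or found at a check.

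**The concern.** The table presents as an exact time something that is partly an upper bound and partly unobserved. A film first found dissolved at the 5 min check could have gone at any point after 2 min, which pushes the summary up. The slowest films contribute nothing, which pulls it down. The net effect depends on how many subjects signal and how many films outlast 5 min. The planned outputs do not show the first of these.

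Protocol 1.3 rests the product's rationale on a film that dissolves on the tongue without water, and Table 14.2.4.1 is the trial's only summary of dissolution time. A reader could quote its mean or maximum as the film's performance when the slowest films are not in it.

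**Working it through.** **No figure to reproduce.** The documents state no dissolution time, no share of subjects who signal and no expected share of undissolved films. Only the check times (1, 2, 5 min) and the recording rules come from protocol 3.1.3.1. The rest is assumed.

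**Error per film.** A check-found time is late by at most 1 − 0 = 1 min at the first check, 2 − 1 = 1 min at the second and 5 − 2 = 3 min at the third. A film beyond 5 min is dropped. The recorded maximum is therefore about 5 min whatever the true maximum is.

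**Error in the summary.** Assume log-normal true times with median m and log-SD s, and no accidental swallows. Let P(x) = Φ(ln(x/m)/s).

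- Share undissolved = 1 − P(5).
- True mean = m·exp(s²/2).
- Recorded mean if all subjects signal = true mean × Φ(ln(5/m)/s − s) / P(5).
- Recorded mean if none signal = [1·P(1) + 2·(P(2) − P(1)) + 5·(P(5) − P(2))] / P(5).

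Take m = 1.5 and s = 0.5, so that P(1) = 0.2087, P(2) = 0.7175 and P(5) = 0.9920. With no signalling the recorded mean is (0.2087 + 1.0176 + 1.3725)/0.9920 = 2.62, against a true mean of 1.5 × exp(0.125) = 1.70. With full signalling it is 1.70 × 0.9718/0.9920 = 1.67.

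| m, s | undissolved at 5 min | true mean | mean, all signal | mean, none signal | median, all signal | median, none signal |
|---|---|---|---|---|---|---|
| 0.75, 0.5 | 0.0% | 0.85 | 0.85 | 1.36 | 0.75 | 1.00 |
| 1.5, 0.5 | 0.8% | 1.70 | 1.67 | 2.62 | 1.49 | 2.00 |
| 2.5, 0.5 | 8.3% | 2.83 | 2.51 | 3.89 | 2.37 | 5.00 |
| 2.5, 0.8 | 19.3% | 3.44 | 2.25 | 3.39 | 2.06 | 5.00 |
| 4.0, 0.8 | 39.0% | 5.51 | 2.72 | 3.98 | 2.66 | 5.00 |

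**Reading the table.**

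- With a quick film and full signalling (row 1) there is no bias.
- In row 2, if 90% signal, the recorded mean is 0.9 × 1.67 + 0.1 × 2.62 = 1.76, a bias of +0.06 min.
- In row 3 with no signalling the bias is 3.89 − 2.83 = +1.06 min.
- In row 4 with no signalling the two errors nearly cancel in the mean (3.39 against 3.44), while the median is doubled (5.00 against 2.50).
- In row 5 with full signalling the bias is 2.72 − 5.51 = −2.79 min.

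**What is not affected.** The proportion of all films dissolved by a given check is the same for signalled and check-found times. A film recorded at 2 min was still present at the 1 min check, and a film recorded at 5 min was still present at 2 min. In row 5 the proportions are 4.2%, 19.3% and 61.0% by 1, 2 and 5 min under either route. Ranking undissolved films above 5 min also repairs the median in that row under full signalling: it becomes 4.00, the true value, instead of 2.66.

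**The case against.** The strongest reply is that the check-time rule is a fallback. Subjects are told to raise a hand, staff must record the actual time, and the listing carries seconds. The mouth-check sentence may even refer to the inspection that confirms a raised hand, which would cost only a short delay. A reader might infer from it that every dissolution time is 1, 2 or 5 min. The documents do not support that, because signalled times are off the grid.

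A reader might also infer that the printed statistics are certainly biased. That is not shown either. Every size above rests on an assumed distribution. The no-signalling column runs against the instruction to subjects, and protocol 1.3 expects rapid dissolution.

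The selection is also partly disclosed. The undissolved and swallowed counts and N stand in the same table, so the proportion dissolved by 5 min can be worked out. Dissolution time is neither a primary nor a secondary variable (protocol 9.1, SAP 7.1), carries no hypothesis and does not enter the bioequivalence comparison. The subjects are healthy, so even an unbiased mean would not measure performance in patients.

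All of this limits the size and weight of the point. It does not remove it. The counts do not correct the statistics below them, nothing marks check-found times as upper bounds, and that slow films drop out of the mean follows from the recording rules and the missing-data rule, although no sentence says so outright.

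**Conclusion.** The point holds as a minor one. The mean, SD, median and maximum in Table 14.2.4.1 describe only films with a recorded dissolution within about 5 min, and any check-found times among them are upper bounds. The cap on the maximum follows from the rules alone. Bias in the mean and median may go either way: from zero to about +1 min, or down to −2.8 min, in the log-normal cases shown. It is negligible if most subjects signal and few films outlast 5 min. The documents do not say how likely that is. Neither the bioequivalence conclusion nor any listed primary or secondary variable is affected.

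**What to change.** In protocol 10.4, SAP 8.5 and Table 14.2.4.1:

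1. Add, for each film administration, the number and proportion of all films fully dissolved by 1, 2 and 5 min. Keep undissolved and accidentally swallowed films in the denominator and show each group separately. Allow a small stated tolerance so that a check made a few seconds late counts at its nominal time.
2. Give the median over all films, with films undissolved at 5 min ranked as >5 min. Report it as >5 min if half or more are undissolved. State how accidentally swallowed films are ranked, since only a lower bound is known for them. Ranking them with the >5 min films is the cautious choice.
3. If the mean, SD and maximum are kept, footnote that they cover only films with a recorded dissolution within about 5 min and that check-found times are upper bounds.
4. Flag signal versus check in Listing 16.2.5.1 only if the source forms record it. Neither document shows that they do.

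An interval-censored estimate is optional. It may need data the CRF is not shown to capture, and censoring accidental swallows assumes that swallowing is unrelated to dissolution speed.

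The cost is one extra table block and a few lines of text, using times already recorded and with no change to trial conduct. The stated dissolution performance may look slower.

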# 3.1.3.2 Reference formulation

One film-coated tablet will be swallowed (without chewing) with 150 mL of still mineral water.

The investigator or deputy will check and confirm that all subjects take the medication appropriately.

Dosing time will be recorded in the specific source documents and in the subject's CRF.

## 3.1.4 Investigational product distribution

The test and reference will be administered by the investigator or by his/her deputy. The IMP will be exclusively used for the present clinical study and will only be administered to the subjects enrolled in the study.

## 3.2 Packaging and labelling

The test primary packaging will be a polyester/foil laminate pouch which is heat sealed.

The formulation labelling will report all the information requested according to the Annex 13 to the Good Manufacturing Practice (published by the Commission in The rules governing medicinal products in the European Community, Volume 4; 8) as follows:

- a. Name, address and telephone number of the sponsor, contract research organisation or investigator (the main contact for information on the product, clinical study and emergency unblinding)
- b. Pharmaceutical dosage form, route of administration, quantity of dosage units, the name/identifier and strength/potency
- c. The batch and/or code number to identify the contents and packaging operation
- d. A study reference code allowing identification of the study, site, investigator and sponsor if not given elsewhere
- e. The study subject identification number/treatment number and the visit/period number
- f. The name of the investigator (if not included in (a) or (d))
- g. Directions for use (reference may be made to a leaflet or other explanatory document intended for the study subject or person administering the product)
- h. "For clinical study use only" or similar wording
- i. The storage conditions

j. Period of use (use-by date, expiry date or re-test date as applicable), in month/year format and in a manner that avoids any ambiguity

Labels will be in local language (Italian).

## 3.3 Storage conditions

The test and the reference will be accurately kept in their pouch until ready to use and stored in the Phase I Unit pharmacy between 20° and 25° C in a dry locked place, sheltered from light.

# 3.4 Drug accountability

Test and reference packed in individual subjects' kits will be provided directly to the investigator by STM Pharma PRO Srl., Italy (§ 16.5), in excess of the amount necessary for the study (at least 25% excess).

The reference will be purchased from the European market.

After receipt of the IMPs, the pharmacist will confirm in writing by signing and dating drug accountability forms.

At the end of the study, used, unused and partially used IMPs will either be destroyed on site (upon written authorisation) or returned to the sponsor, after final reconciliation of all IMP accountability.

